6.4 Statistical data quality control

Both an Intention To Treat (ITT) and a Per Protocol (PP) analysis will be performed.

Descriptive statistics will be provided for baseline variables including demographic and anthropometric values. The number and percentage of AEs will be tabulated by verbatim term and for categories via ICD-9. Adverse events will be defined as pre-treatment or treatment emergent if pre-treatment AEs are reported for that study.

7.Data Handling and Record Keeping

Clinical data (including AEs and Concomitant Medications) will be captured into a paper CRF. It will be the responsibility of the PI and monitor to ensure the completeness and accuracy of the data.

All videos from the FMD scans will be evaluated by experts (Quipu srl, [name]) in dedicated software (FMD studio). The expert will also provide comments on the quality of the scans made by the sonographers and note when adjustments of the baseline diameter were made. It is to be noted that all FMD assessment will be made by a fully blinded expert assessor.

All site staff must ensure that the subject's anonymity will be maintained. On all documents that are to be submitted to external laboratory, subjects must be identified only by an identification code and not by their names. The PI or designee must keep a separate confidential enrolment log that matches identifying codes with the subject's names and addresses. The PI or designee must maintain these documents at the site.

It is the responsibility of the PI or designee to maintain adequate study records. All documents must be archived in a secure place and treated as confidential material.

All the patients' data will be treated according to Data Protection Code - Legislative Decree no. 196/2003.

8. Quality Standards

It is the responsibility of the PI to ensure that the study is conducted in accordance with the principles of Good Clinical Practice, the 2008 version of the Declaration of Helsinki and according to applicable local laws and regulations concerning studies conducted on human subjects, which are outside of the definition of a medicinal product or medical device.

Quality assurance audits may be performed by any ethics committee or regulatory authority during the course of the study or at study completion.

9. Ethics and Informed Consent

The PI or designee must submit a copy of the protocol, subject information sheet and consent form to an Independent Ethics Committee or Institutional Review Board who must provide written approval before study specific procedures commence. The IEC/IRB must also approve any other information that is given to subjects such as advertisements and may require other documents such as study product documentation.

Any modification to the agreed protocol must be approved in writing by the IEC/IRB. Written approval must be obtained from the IEC/IRB before any amendment is implemented, unless immediate change is required to eliminate hazards to the subjects or when the change(s) involves only logistical or administrative aspects of the study (e.g., change of telephone number(s)).

The PI or designee must obtain informed consent from each subject participating in the study, after explanation of the aims, methods, benefits and potential hazards of the study. The consent must be obtained before any study-specific procedures are performed. It must be made completely and unambiguously clear to each subject that they are free to refuse to participate in the study, or that they can withdraw their consent at any time and for any reason, without incurring any penalty or withholding of treatment. The subject must be given their own copy of the information sheet and signed consent form. The original signed informed consent must be kept on file by the PI or designee.

10. References

- Bazzichi L, Ghiadoni L, Rossi A, Bernardini M, Lanza M, De Feo F, Giacomelli C, Mencaroni I, Raimo K, Rossi M, Mazzone AM, Taddei S, Bombardieri S.
Osteopontin is associated with increased arterial stiffness in rheumatoid arthritis.
Mol Med. 2009 Nov-Dec;15(11-12):402-6.
- Bernini G, Galetta F, Franzoni F, Bardini M, Taurino C, Bernardini M, Ghiadoni L, Bernini M, Santoro G, Salvetti A.
Arterial stiffness, intima-media thickness and carotid artery fibrosis in patients with primary aldosteronism.
J Hypertens. 2008 Dec;26(12):2399-405.
- Cannon RO 3rd.
Role of nitric oxide in cardiovascular disease: focus on the endothelium.
Clin Chem. 1998 Aug;44(8 Pt 2):1809-19. Review. Erratum in: Clin Chem 1998 Sep;44(9):2070.
- Cohen Marc Maurice.
Ubiquinol (Reduced Coenzyme Q10): A novel yet ubiquitous nutrient for heart disease.
J Adv Nutr Hum Metab 2015; 2: e647

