3.3 Selection of Subjects

3.3.1 Planned number of subjects

Sample size: 51 (17 per group), healthy, adult males and females.

In females, FMD varies with the hormonal cycle. Therefore, to avoid such complications, the study will be conducted in post-menopausal female subjects only.

Subjects will be recruited from subjects referred as outpatients to U.O.C. Laboratorio Analisi – POR I.N.R.C.A. Ancona, Italy. Selection of suitable subjects will be made according to the inclusion and exclusion criteria described in the following sections.

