5.1.2 Study Specific Expected Adverse Event

While trained and experienced nurses/phlebotomists will draw the blood with utmost care, there is a possibility that some of the subjects may experience haematoma (bruise or collection of blood under the skin with minor swelling in the area, which may last for few days), fainting or injury to the nerves after venipuncture. Moreover, temporary occlusion of arm during FMD measurement may cause transient hematoma, discomfort or paresthesia. These symptoms will not be recorded as adverse events.

Rarely, ubiquinol may cause mild gastrointestinal upset, decrease in appetite, nausea, vomiting, diarrhea or constipation and rash.

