5.3 Severity and Relatedness of Adverse Events

An AE will be recorded only once, with the most extreme severity. Severities are defined as:

Mild	Awareness of symptoms which require minimal or no treatment and do not interfere with daily activity
Moderate	Discomfort or low level of interference which is enough to interfere with but not prevent daily activity
Severe	Interrupted or unable to perform usual daily activity and usually requires treatment.

The likelihood that the AE was related to the study product or study procedure is defined as;

Not Related	The AE is clearly due to an alternative cause, even if this cannot be definitely identified. Alternative causes include disease or environmental factors.
Unlikely	A connection between the AE and the study product or procedure is unlikely. 
• The AE has a relationship in time to the study product or procedure• An alternative cause (e.g. disease or environmental factors) is the most likely explanation, even if this cannot be identified.
Possibly	A connection between the AE and the study product or procedure cannot be ruled out with certainty. 
• The AE has a relationship in time to the study product or procedure

	
 • An alternative cause (e.g. disease or environmental factors) seems likely or possible or there is significant uncertainty about the cause of the AE.
Probably	
There is a high degree of certainty that the AE is related to the study product or procedure.
 
 • The AE has a relationship in time to the study product or procedure • A possible alternative cause may be present. • AE disappears or decreases on withdrawal or reduction of study product or procedure (if performed).
Definitely	
The AE is clearly related to the study product or procedure.
 
 • There is a strong relationship in time • An alternative cause is unlikely • AE disappears or decreases on withdrawal or reduction of study product or procedure (if performed)

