5.4 Reporting of Adverse Events

All AEs will be recorded in the CRF. All AEs will be coded using ICD-9 and reported according to local regulations.

It should also be remembered that, referring to the legislation currently in force, doctors are obliged to notify any suspected adverse reaction of which they become aware in their clinical practice, by completing the appropriate specific reporting form.

Once completed, this form will be sent to the Pharmacovigilance team responsible for the relevant health institution the Investigator belongs to.

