6.1 Sample Size Calculation

Sample size calculation is carried out with use of G*power Software.

The parameters used to compute sample size for this study were taken from the reference article by Gao et al 2012, a meta-analysis of 5 randomized controlled trials.

Mean and SD taken from the article by Watts GF et al 2002, one of the RCT mentioned in reference article (see fig. 2 in the article by Gao et al), were considered as appropriate values to be taken into account: considering group one mean and SD as 1.6 (1.16) and second group mean and SD as -0.4 (2.24), with 80% power and 5% two-sided significance level, 14 subjects are required for one group.

In this study, considering a 20% dropout rate, a total of 52.5 subjects should have been enrolled; a sample size equal to 51 subjects was deemed as appropriate.

It is to be noted that in this study the minimum increment of FMD reached with the number of patients provided for each group is to be considered as equal to 1.6% (according to Figure 2 shown in Gao et al, in particular by referring to the study of Watts, which provides a sample size similar to ours).

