6.2 Definition of Analysis Population

All subjects receiving at least one study product will be used for safety analyses. All subjects with at least 1 FMD measurements will be part of the intention-to-treat population. All subjects with no major deviation from the protocol will form the per-protocol population. All FMD measurements with acceptable quality will be used for analyses. Decision on the per-protocol population and FMD measurement quality will be made during blind review and documented.

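### Section 6.4 makes adverse events, not subjects, the unit of the safety table and gives no subject denominator, although 6.2 defines the safety population by subjects (minor)

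*Protocol*

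**What the plan says.** The only rule in the protocol for summarising adverse events is in section 6.4: "The number and percentage of AEs will be tabulated by verbatim term and for categories via ICD-9". The next sentence there adds a split into pre-treatment and treatment-emergent events, where pre-treatment events are reported. The text does not mention subjects with an event, the denominator of the percentage, or presentation by treatment group.

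The safety population, by contrast, is a set of people (section 6.2): "All subjects receiving at least one study product will be used for safety analyses".

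Three other provisions bear on the point:

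- Coding (section 5.4): "All AEs will be coded using ICD-9 and reported according to local regulations". Section 3.8.3 also requires ICD-9 coding.
- Counting (section 5.3): "An AE will be recorded only once, with the most extreme severity".
- Expected product effects (section 5.1.2, with a similar list in 3.8.3): "Rarely, ubiquinol may cause mild gastrointestinal upset, decrease in appetite, nausea, vomiting, diarrhea or constipation and rash".

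Section 3.8.3 assesses safety and tolerability through adverse events alone. Section 3.3.1 plans the group size: "Sample size: 51 (17 per group), healthy, adult males and females".

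**The concern.** A reader of the safety table wants to know how many of the people given each dose had an event, compared with placebo. A count of events, or a percentage built on events, does not answer that. The expected effects in 5.1.2 make the gap a practical one: gastrointestinal upset, nausea, vomiting and diarrhoea can occur together in one person, so several events can come from one subject.

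At stake is whether the descriptive tolerability table can be read. In groups this small, one subject with several complaints can make up most of a row. The primary FMD analysis is not affected, nor is what data are collected.

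**Working it through.** **The plan's own figure.** The protocol gives no adverse event rates, so there is no safety figure to reproduce. The group size used below comes from the FMD calculation in 6.1: "considering group one mean and SD as 1.6 (1.16) and second group mean and SD as -0.4 (2.24"), and "with 80% power and 5% two-sided significance level, 14 subjects are required for one group".

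- Common SD = √((1.16² + 2.24²)/2) = 1.784. Standardised difference = (1.6 − (−0.4))/1.784 = 1.121.
- A two-sample t-test, two-sided 5%, 80% power, gives n = 13.52, rounded up to 14 per group. Power at 14 is 81.5%.
- With 20% dropout: 3 × 14/0.80 = 52.5. The protocol settles on 51, that is 51/3 = 17 per group.

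The size reproduces. It was set for FMD, not for safety. The 17 is a planned figure: section 3.4 uses simple randomisation, so actual group sizes may differ.

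**Check 1: a percentage of events is not a risk.** The counts are illustrative. Suppose a ubiquinol group has 10 events, of which 5 are gastrointestinal and come from 5 different subjects. Placebo has 2 events, of which 1 is gastrointestinal.

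| | Ubiquinol group | Placebo |
|---|---|---|
| Gastrointestinal events, number | 5 | 1 |
| As % of events | 5/10 = 50% | 1/2 = 50% |
| Subjects affected | 5/17 = 29.4% | 1/17 = 5.9% |

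The percentage column shows no difference. The number column does (5 against 1). So here the percentage misleads, but the table as a whole does not conceal the imbalance.

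**Check 2: events do not identify subjects.** Keep the same ubiquinol group, but let all 5 gastrointestinal events be distinct complaints of one subject, and assume the ICD-9 category is broad enough to hold them all.

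| | Five subjects, one complaint each | One subject, five complaints |
|---|---|---|
| Events, number | 5 | 5 |
| As % of events | 5/10 = 50% | 5/10 = 50% |
| Subjects affected | 5/17 = 29.4% | 1/17 = 5.9% |

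Both columns required by 6.4 are identical, and only the subject count separates the two situations. With three complaints instead of five, the contrast is 3/17 = 17.6% against 1/17 = 5.9%.

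**Check 3: does another denominator rescue the sentence?** If the percentage were taken over subjects treated but the numerator stayed as events, check 2 would give 5/17 = 29.4% in both situations. The numerator is the fault, whichever denominator is meant.

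**Check 4: what subject-level reporting could show.** Using Fisher's exact test, two-sided, at 17 against 17, p ≤ 0.05 needs at least 5/17 against 0/17 (p = 0.0445) or 7/17 against 1/17 (p = 0.039). The 5/17 against 1/17 of check 1 gives p = 0.17. Power, assuming a 5% placebo rate (an assumption, not a protocol figure):

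| True rate on ubiquinol | One dose vs placebo (17 vs 17) | Both doses pooled (34 vs 17) |
|---|---|---|
| 10% | 1% | 1% |
| 20% | 12% | 18% |
| 30% | 35% | 53% |
| 40% | 61% | 80% |

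**The case against.** The strongest case against runs as follows.

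- **ICD-9 categories already gather differently worded complaints.** This stands. The sentence requires coded categories as well as verbatim terms, so it would be wrong to say that verbatim rows scatter the gastrointestinal effects beyond recovery. Grouping does not settle the unit, however: check 2 is already at category level.
- **Each event is recorded once.** This partly stands. The rule limits inflation from repeated reports of one complaint, though whether it covers separate recurrences is unclear. It does not merge nausea, vomiting and diarrhoea in one subject.
- **The denominator is inferred.** This stands as a matter of wording: 6.4 states none, and it does not exclude subject counts. But it does name events as what is counted, and check 3 shows that the denominator alone does not cure that.
- **The number column would reveal the imbalance.** True for check 1, not for check 2.
- **Table layout belongs in the SAP.** Largely fair, and a reason to grade the point low. Severity and relatedness breakdowns, a dedicated gastrointestinal row and the placing of verbatim terms in listings are layout matters and are not raised here. The unit is different, because the protocol has stated one.

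A reader might infer the stronger claim that the tables, as specified, cannot show whether ubiquinol causes the listed effects because events are counted. The documents do not support it. Event counts carry some information and subject counts can be derived from the CRF. The protocol also calls these effects rare, and check 4 shows that 17 per group limits any causal reading whatever the unit.

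**Conclusion.** The point holds as a minor one. Section 6.4 fixes events as the unit of the number and percentage, without a subject denominator, while 6.2 defines the safety population by subjects. A table built literally to that wording can misstate how many subjects were affected: in the example, identical entries stand for 6% or 29% of a group of 17.

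This rests on the plain reading of the sentence, on illustrative counts, on the planned 17 per group, and on subjects having more than one distinct complaint. If every subject had at most one event per category, event and subject counts would coincide and only the denominator would remain open.

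Safety is neither a primary nor a secondary endpoint, the reporting is descriptive, and no data are lost. Subject-level reporting makes the table interpretable. It does not turn the trial into a test of tolerability: under the assumed 5% placebo rate, power for one dose against placebo is about 1% to 12% at true rates of 10% to 20%.

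**What to change.** Replace the tabulation sentence in 6.4 with wording to this effect: for the safety population and by treatment group, the number and percentage of subjects with at least one treatment-emergent adverse event will be reported, overall and by ICD-9 category, with the number of events alongside; the denominator is the number of subjects in the safety population in that group.

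The cost is one sentence and an adjusted table. No new data are needed, since events are already recorded and coded for each subject in the CRF.
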